3.2 Secondary

|--|

•

- 1. Secondary objective 1-:
 Estimate mean total fixed and monthly expenditures to mitigate SARS-CoV-2 transmission risk, overall and for mutually exclusive groups of practitioners identified by the primary objective analysis
- 2. Secondary objective 2: Assess mean levels of comfort and/or confidence with available information and guidelines for infection control, approaches used to mitigate SARS-CoV-2 transmission risks, and the financial impact of mitigation, overall and for mutually exclusive groups of practitioners identified by the primary and secondary objective analyses
- 3. Secondary objective 3:
 Disseminate the Wave 1
 Rapid Report and
 conduct informational
 Rapid Report Webinars
 with network
 practitioners, and assess
 the impacts of Report
 dissemination on
 changes in practitioners'
 mitigation approaches,
 mitigation costs, and
 comfort levels, overall
 and for different
 practitioner subgroups
- Secondary objective 4: Establish a modular infrastructure to support the design and conduct of additional multilevel clinical and implementation science research.

- I. The cost to dental practices for coronavirus mitigation may be significant and may influence the approaches used by practitioners and practices. PPE and other mitigation costs will be obtained via the financial costs section of the survey
- Dental care delivery creates aerosols as part of routine service delivery. Practitioner's level of comfort with treating patients with known or asymptomatic COVID-19 is an important concern that may affect their mitigation choices.

This study involves

- practitioners in the study by incorporating Rapid Results reporting and informational webinar attendance following each wave of the questionnaire. This provides an opportunity for participants to gain knowledge quickly in a rapidly changing environment, which may impact the mitigation approaches they use. We will provide Rapid Report results using the practitioner's page in the Hub, and schedule webinars to enhance discussion and support peer-to-peer information sharing. We will compare Wave 1 and Wave 2 responses to assess the impacts of the reports and webinar attendance on changes in mitigation approaches
- The CORE Registry programming and data collection capabilities will be developed to support the additional of new modules

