We will recruit a target 38% of non-Hispanic white and Asian practitioners, groups that are well-represented in the network. We plan to enroll a target of 45% for under-represented minority (URM) practitioners, including Hispanic/Latinos, Black/African Americans, Alaska Native and Native Americans, and Native Hawaiian/Pacific Islanders, multi-race, and others. We will include race-ethnicity recruitment rates in our reports and use tailored follow-up emails to help promote URM recruitment and include these data in reports for regional NCs.

Participant Incentives

We do not plan to provide financial remuneration for study participants. While we provide no monetary remuneration, we believe the importance of the topic and the inclusion of rapid reporting and webinars for participating practitioners will drive recruitment. Additionally, respondents who request Continuing Education credit by answering affirmatively to the last question in the CRQ1 will receive 0.5 hour CE credit

from the UAB School of Dentistry Continuing Education Department. Depending on available resources, CE Credit for completing the last question in the CRQ2 survey may also be provided.

Participating practitioners will receive Wave 1 and Wave 2 CORE Registry Rapid Reports (CRR1 and CRR2) and encouragement to attend CORE Registry Study results webinars.

Practitioners attending a CORE Registry Results Webinar (CRW1 or CRW2) may receive 1.0 CE credit from the UAB School of Dentistry Continuing Education Department for each hour of webinar attendance.

In addition, depending on analyses of Wave 1 results, the study team may decide to conduct a test-retest process for a small sample of Wave 2 questionnaire completers. We expect a retest would include a target of approximately 20-40 (max of 60) participants.

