6.2 Phase 2 – CRQ1 analysis and initial result dissemination

- CRQ1 responses are cleaned and analyzed by the CORE study team.
- Develop a CORE Registry Results Report Wave 1 (CRR1) and distribute to participating practitioners (CRQ1 respondents) through their individual Hub home pages. The CRR1 highlights initial CRQ1 summary statistics and CART analyses of SARS-CoV-2 transmission risks mitigation.
- Organize and deliver 3-5 CRR1 webinars (CRW1) for participating practitioners to disseminate and discuss CRR1 results and implications for practice. Webinar schedules will be developed in consultation with NCC and ARC staff. Webinar recruitment emails will be sent centrally by the NCC and regional NCs.
- Document receipt of CRR1 and attendance for 1≥ CRW1; provide CE for attendees.

6.3 Phase 3 – Conduct CORE Registry Questionnaire Wave 2 (CRQ2) (T2 = T1 + ~4 months (+~6-8 weeks))

- Conduct Wave 2 (CORE Registry Questionnaire Wave 2, CRQ2) with a target of 38% of U.S. dentists and hygienists enrolled in the Network at the time of Wave 2, over 6-8 weeks.
- Emphasize recruitment of CRQ1 respondents to maximize comparisons between Wave 1 and Wave 2 data.

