7. STUDY PROCEDURES/EVALUATIONS

Questionnaire Development

The primary sources of information used to develop the Wave 1 survey include the CDC's interim and updated guidance for infection prevention and control for healthcare personnel, and guidance for dental facilities and staff, the American Dental Association Health Policy Institute recommendations and scientific webinars, OSHA guidelines, and the Organization for Safety, Asepsis, and Prevention (OSAP) in partnership with DentaQuest.

Drafts of the survey questions, responses, and content flow were developed by the study team and reviewed by NIDCR, the Data Committee, the Biostat Core, and Practitioner Executive Committee prior to finalizing the survey instrument. As part of the review process, the survey instrument was assessed to ensure it is psychometrically sound and to ensure the data collected will allow for adequate evaluation of study objectives.

The Wave 2 survey repeats survey items from Wave 1 and includes additional items to assess participant receipt of the Wave 1 Rapid Report, Wave 1 webinar attendance, and impacts of these activities on SC2 mitigation approaches and comfort levels. Depending on scientific development and guidelines related to SC2 transmission risks, some individual survey items or responses may be revised.

The Wave 2 survey will undergo the review process described above for the Wave 1 survey.

Questionnaire User Testing

The NCC will perform internal testing of the electronic study questionnaire and include testing internet browser compatibility. Study team members (e.g. PI, National Network Director, Node Directors, etc.) will be given the opportunity to externally test the website prior to administration to study participants.

Questionnaire Administration

Eligible participants will be identified from their responses to the network's enrollment questionnaire.

A waiver of documentation of signed informed consent for participants who complete the electronic questionnaire will be requested. Consistent with regulations outlined by the University of Alabama at Birmingham IRB and regional/local IRBs, information about the study will be provided to all eligible participants in the initial email invitation regarding the upcoming invitation to participate in the study. Completion of the questionnaire will indicate tacit consent.

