Objective 3 (secondary): Disseminate the Wave 1 Rapid Report and conduct informational Rapid Report Webinars with network practitioners, and assess the impacts of Report dissemination on changes in practitioners' mitigation approaches, mitigation costs, and comfort levels, overall and for different practitioner subgroups

Changes in virus mitigation approaches will be assessed by comparing Wave 2 with Wave 1 data for practitioners who complete both surveys. Wave 2 survey includes questions for assessing the impact of Rapid Reports and webinars from Wave 1 on practitioner decision making.

Changes in comfort levels will also be assessed, which is relevant for respondents who may not change their mitigation approach but may have improved confidence in the approaches they use. These would otherwise go unmeasured. We will use CART analysis to separately identify mutually exclusive groups of practitioners with common overall levels of comfort with their existing risk mitigation approaches from Questionnaires 1 and 2, and practitioners who report changes in comfort levels between the two surveys.

Objective 4 (secondary): Establish a modular infrastructure to support the design and conduct of additional multilevel clinical and implementation science research.

We are enabling additional modules to be incorporated into the CORE Registry through NCC participation with newly funded study teams who are addressing COVID-related research topics. This will involve developing common measures, integrating study data into the Registry structure, and other activities as necessary given available resources. The survey date will support numerous additional analyses, which will be developed as time and resources allow.

The objective 4 outcome will be measured as the successful integration of one or more additional COVID-related network study. Capability for expansion is designed into the

Registry as the CORE Registry study modules are built.

Missing data. Data from incomplete questionnaires may be included in data analyses. Depending on the extent of missing data and available resources for analyses, the study team may consider statistically appropriate methods for imputing missing information.

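### Secondary Objective 3 asks for the impact of the Wave 1 report and webinars, but its stated Wave 1 to Wave 2 comparison cannot separate that impact from change that would have occurred anyway

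*Protocol*

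**What the plan says.** Protocol section 11.2, Objective 3 (secondary), states the aim in causal terms: to "assess the impacts of Report dissemination on changes in practitioners' mitigation approaches, mitigation costs, and comfort levels". The analysis of change follows: "Changes in virus mitigation approaches will be assessed by comparing Wave 2 with Wave 1 data for practitioners who complete both surveys". The next sentence of that section adds that the Wave 2 survey also asks about the impact of the reports and webinars on decision making.

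The objectives table in section 3.2 ties the aim to the comparison directly: "We will compare Wave 1 and Wave 2 responses to assess the impacts of the reports and webinar attendance on changes in mitigation approaches".

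On who is exposed, section 6.2 plans to develop CRR1 and "distribute to participating practitioners (CRQ1 respondents) through their individual Hub home" pages. It also plans to "Document receipt of CRR1 and attendance for 1≥ CRW1; provide CE for attendees". Section 7 says the Wave 2 survey has "additional items to assess participant receipt of the Wave 1 Rapid Report, Wave 1 webinar attendance", together with items on the impact of these activities.

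On background change, section 2.1 expects agencies and professional bodies to go on issuing new guidance, and section 3.2 describes conditions as changing fast. Guideline and incidence data are collected at each wave (sections 3.2, 11.2 and 12).

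**The concern.** A within-person difference between two waves estimates an impact only if nothing else would have moved the answers between them. The protocol says the opposite. The comparison is also confined to practitioners who were all sent the report, so it has no group showing what would have happened without distribution. If the difference is read as the impact of dissemination, as section 3.2 invites, practitioners and the funder could be told that rapid reporting changed practice when the data cannot show it. The reverse error is also possible: a real benefit could be hidden by background relaxation of precautions.

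**Working it through.** **Step 1: who is in the comparison.** Completing both surveys requires completing CRQ1 (section 11.2). All CRQ1 respondents are sent CRR1 (section 6.2). So every member of the analysis set was sent the report, and being sent it does not vary within the set.

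**Step 2: what the difference estimates.** Let d be the average effect of report and webinars, and s the average change that would have occurred anyway. Then

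mean(Wave 2 − Wave 1) = d + s.

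One quantity is observed and two are unknown. With d = 0 the comparison estimates s.

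**Step 3: sample size.** The protocol states no figure for Objective 3. Its overall figure reproduces: 0.38 × 5,300 = 2,014, against about 2,000 in section 11.1. The number answering both waves is not given, so I assume 40, 60 or 80% of 2,014: 806, 1,208 or 1,611.

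**Step 4: how small a background change would show.** Take a yes/no mitigation approach and set d = 0. Assume 20 to 30% of practitioners give different answers in the two waves (discordance D). With n completers, a McNemar-type test at two-sided 0.05 has SE₀ = √(D/n) under no change and SE₁ = √((D − s²)/n) under a net change s. The probability of a significant result is approximately

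Φ((s − 1.96·SE₀)/SE₁),

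plus a negligible opposite tail when s is above zero.

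Worked case: n = 806, D = 0.3, s = 0.05. SE₀ = √(0.3/806) = 0.0193 and SE₁ = √(0.2975/806) = 0.0192. Then (0.05 − 0.0378)/0.0192 = 0.63, giving 0.74.

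| Background change s | n = 806 | n = 1,208 | n = 1,611 |
|---|---|---|---|
| 0 | 0.05 | 0.05 | 0.05 |
| 3 points | 0.34–0.48 | 0.48–0.65 | 0.59–0.77 |
| 5 points | 0.74–0.89 | 0.89–0.97 | 0.96–0.995 |
| 10 points | ≥0.999 | about 1 | about 1 |

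Each range runs from D = 0.3 to D = 0.2.

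**Step 5: what an exposure contrast would give.** Let q be the fraction attending a webinar (or with documented receipt), assumed 10 to 50%. Compare change between exposed and unexposed. A background change common to both groups cancels. The difference in change detectable with 80% power is

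(1.96 + 0.84) × √(D·[1/(nq) + 1/(n(1 − q))]).

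- Best case (n = 1,611, q = 0.5, D = 0.2): 2.80 × √(0.2 × 4/1,611) = 0.062.
- Middle case (n = 1,208, q = 0.3, D = 0.3): 0.096.
- Worst case (n = 806, q = 0.1, D = 0.3): 0.180.

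So about 6 to 18 percentage points. Relative to the before-after interval, the contrast is wider by 1/√(q(1 − q)): 2.0 times at q = 0.5, 2.2 at 0.3 and 3.3 at 0.1.

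**The case against.** - **The before-after difference is not the only source of impact data.** This is right: the Wave 2 survey asks about impact directly. But a practitioner's own attribution measures perceived impact. It does not show what that practitioner would have done otherwise.
- **Being sent a report is not the same as being exposed to it.** This also stands. CRR1 is posted to Hub pages, reading it and attending webinars are voluntary, and receipt and attendance are recorded. A reader might infer that the analysis set contains nobody unexposed. That holds for distribution only. The variation makes a better analysis possible, but the stated comparison does not use it. Section 4 allows CART to explore factors associated with change between waves, without naming receipt or attendance among them.
- **No text says that all change will be credited to the report.** True. A reader might infer that it will, but the secondary outcome is labelled neutrally as change between waves, and guideline and incidence data are collected. The supportable statement is that the two cannot be separated by the stated comparison.
- **Model detail belongs in the SAP, which was not available for this review.** The adjustment set and weights do. But section 3.2 already fixes the Wave 1 to Wave 2 comparison as the means of assessing impact, and that is a stated method that does not reach its stated aim.
- **The study tests no hypotheses (section 11.1).** This weakens the significance probabilities as a measure of harm, and they are offered only as a scale. An estimate of d + s is confounded whether or not it is tested.
- **An attendance contrast is self-selected.** It is. For that reason it supports an association and not an effect.

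**Conclusion.** The point holds in a limited form. For Objective 3, the stated comparison of waves among practitioners who completed both surveys cannot distinguish an effect of the report or webinars from concurrent change. The protocol's own account of the period makes such change likely. The perceived-impact items do not close the gap.

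The structural argument (steps 1 and 2) rests on the protocol text alone. The sizes rest on assumptions the protocol does not supply: 40 to 80% of 2,014 answering both waves, 20 to 30% discordance and 10 to 50% attendance. Within those ranges, a background change of 5 percentage points with no report effect would be significant with probability 0.74 to 0.995.

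Severity is moderate. One secondary objective is affected; the primary objective and the data collection are not.

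**What to change.** In sections 3.2 and 11.2, separate three quantities:

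1. The Wave 2 minus Wave 1 difference, reported as change.
2. The Wave 2 impact items, reported as perceived impact.
3. For the impact question, the difference in change between practitioners with and without documented CRR1 receipt, and between webinar attenders and non-attenders. Adjust for the Wave 1 value of the outcome, Enrollment Questionnaire characteristics, and local incidence and guideline changes. Describe the result as an association.

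A comparison with practitioners who answered Wave 2 only should be supplementary at most. They have no Wave 1 value, and they may be few and selected because Wave 2 recruitment concentrates on Wave 1 respondents. Their non-exposure is not assured either, since Objective 3 speaks of webinars for network practitioners generally.

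The cost is a change of wording and analysis, using data already planned. The intervals will be about 2 to 3.3 times as wide as the before-after interval under the attendance range assumed above. Residual self-selection into receipt and attendance must be stated as a limitation. If almost everyone has documented receipt, the receipt contrast will be uninformative and the webinar contrast will have to carry the question.

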12. SOURCE DOCUMENTS AND ACCESS TO SOURCE DATA/DOCUMENTS

Source data/documents will be maintained by the NCC for this study. The NCC will program the electronic questionnaires into their EDC on the HUB website. Participants will be sent an email invitation with a direct link to the electronic questionnaire. After completion of the electronic questionnaire, data will be available through the EDC.

Only study personnel i.e. NCC, PI and designated study team members will have access to the data. All research computers and associated study documents will be password-protected and maintained in compliance with ICH E6, Section 4.9 and regulatory and institutional requirements for the protection of confidentiality of subjects. Study staff will permit authorized representatives of NIDCR and regulatory agencies to examine (and when required by applicable law, to copy) research records for the purposes of quality assurance reviews, audits, and evaluation of the study safety, progress and data validity.

The PI and designated study team members will create an MS Access database of federal, state, and professional dental practice and workplace regulations, and clinical practice guidelines and recommendations related to the mitigation of SARS-CoV-2 transmission risks at dental practice settings. The study team will maintain and periodically update the Access database. Through a partnership with ASTDD, the Study team will provide access to the Policy database to state dental directors.

The source documents for this study are:

- Electronic study questionnaire administered through the NCC EDC on the HUB website
- Selected data collected on the National Dental PBRN Enrollment Questionnaire (gender, year of birth, race/ethnicity, present practice type, year of dental school graduation, full time or part time practice, practice type (dentist, hygienist, dental therapist) and specialty general practitioner or specialist,)
- State and local epidemiologic data on COVID-19 incidence and hospitalization are obtained through publicly available sources, including the Johns Hopkins University COVID-19 Tracking Website and state and local departments of health.
- Federal, state, and professional society clinical practice guidelines and recommendations relevant to coronavirus transmission risk mitigation are

obtained from publicly available sources and maintained in an MS Access Database by the Study team and NCC for analysis purposes. Sources include the CDC, World Health Organization, American Dental and Dental Hygiene Associations, the Association of State and Territorial Dental Directors, and state dental associations. Applicable federal and state regulations are obtained from Occupational Safety and Health Administration, state departments of health, and state licensing boards.

For the Quality Control (QC) and Quality Assurance (QA) activities associated with data collection and processing, procedures will be developed to include automatic data quality checks in the EDC for the questionnaire and the processes related to data

accuracy and completeness. The EDC will be programmed with edit checks and

response limiters to reduce data response errors.

13. QUALITY CONTROL AND QUALITY ASSURANCE

14. ETHICS/PROTECTION OF HUMAN SUBJECTS

14.1 Ethical Standard

The PI will ensure that this study is conducted in full conformity with the principles set forth in The Belmont Report: Ethical Principles and Guidelines for the Protection of Human Subjects of Research, as drafted by the US National Commission for the Protection of Human Subjects of Biomedical and Behavioral Research (April 18, 1979) and codified in 45 CFR Part 46 and/or the ICH E6.

14.2 Institutional Review Board

The protocol, informed consent form(s), recruitment materials and all participant materials will be submitted to the National Dental PBRN Central Institutional Review Board (IRB) for review and approval. The UAB IRB for Human Use serves as the National Dental PBRN Central IRB. Approval of both the protocol and the consent form(s) must be obtained before any participant is enrolled. Any amendment to the protocol will require review and approval by the IRB before the changes are implemented in the study.

For those study investigators requiring IRB approval by their institutions, the study institution PI will submit for IRB approval and provide the Central IRB with the appropriate approved IRB documents.

14.3 Informed Consent Process

A waiver of documentation of signed informed consent for practitioners who complete the electronic questionnaire will be requested. Consistent with regulations outlined by the National Dental PBRN Central IRB, information about the study will be provided to eligible practitioners in an initial study invitation email as well as in the electronic questionnaire prior to the start of the questionnaire. Initiation of the questionnaire will provide a record of tacit consent.

14.4 Exclusion of Women, Minorities, and Specific Age Groups

National Dental PBRN dentists of any age, sex/gender or racial/ethnic group may participate if they meet the eligibility criteria.

14.5 Participant Confidentiality

Participant confidentiality is strictly held in trust by the investigators, study staff, and the study sponsor and their agents. The study protocol, documentation, data, and all other information generated will be held in strict confidence. No information concerning the study, or the data will be released to any unauthorized third party without prior written approval of the study sponsor.

Practitioners' pre-assigned identification numbers (PIDs) (practitioner IDs assigned by the National Dental PBRN) will be used to maintain study records and organize data

files. A file linking participants' names with their unique identification number will be kept in a password-protected file by the NCC.

The study monitor or other authorized representatives of the NIDCR may inspect all study documents and records required to be maintained by the investigator.

Certificate of Confidentiality

To further protect the privacy of study participants, the Secretary, Health and Human Services (HHS), has issued a Certificate of Confidentiality (CoC) to all researchers engaged in biomedical, behavioral, clinical, or other human subjects research funded wholly or in part by the federal government. Recipients of NIH funding for human subjects research are required to protect identifiable research information from forced disclosure per the terms of the NIH Policy (https://humansubjects.nih.gov/coc/index). As set forth in 45 CFR Part 75.303(a) and NIHGPS Chapter 8.3, recipients conducting NIHsupported research covered by this Policy are required to establish and maintain effective internal controls (e.g., policies and procedures) that provide reasonable assurance that the award is managed in compliance with Federal statutes, regulations, and the terms and conditions of award. It is the NIH policy that investigators and others who have access to research records will not disclose identifying information except when the participant consents or in certain instances when federal, state, or local law or regulation requires disclosure. NIH expects investigators to inform research participants of the protections and the limits to protections provided by a Certificate issued by this Policy.

Confidentiality of Data Sharing

As described in section 16, it is NIH policy that the results and accomplishments of the activities that it funds should be made available to the public (see https://grants.nih.gov/policy/sharing.htm). PIs and funding recipient institutions will ensure that all mechanisms used to share data include proper plans and safeguards to protect the rights and privacy of individuals who participate in NIH-sponsored research.

